9. POTENTIAL BENEFITS

No immediate or direct benefits to patients participating in this study are expected. However, it is our hope that participants will have reduced adherence barriers and learn better disease management skills. The information obtained from this study can ultimately be used to increase

knowledge in the scientific community about how to improve adherence barriers in youth with T1D.

10. POTENTIAL RISKS, DISCOMFORTS, INCONVENIENCES, & PRECAUTIONS

There are minimal potential risks/discomforts/inconveniences to participants in this study, no greater than those encountered in routine behavioral assessment and clinical care. There are no medical risks. All the questionnaires have been used in research, including our own, without any reported negative effects; however, it is possible that a small group may feel uncomfortable responding to questions. Participants may decline answering questions that cause them to feel uncomfortable and will be reminded of this prior to each study visit. Participants may also withdraw from the study at any time and will be informed of this right during the consent/assent process.

If a participant is distressed by any study procedures, the site PI or designee will be contacted immediately to assess the situation. The study PI or their designee will provide appropriate referrals and/or intervention. Safety procedures for suicidal ideation and reports of abuse/neglect are delineated in our safety monitoring committee plan (See Appendix E). In both cases and similar to above, the study PI or their designee at each site will be contacted immediately and he/she will assess the risk profile of the caregiver and/or adolescent participant with subsequent recommendations based on the level of risk. Further, the PHQ-8 assesses participants for depressive symptomology. Though the suicidal ideation item has been removed from this version (e.g. PHQ-8 not PHQ-9) for the purposes of the current study, a significant elevation on the PHQ-8 suggests the participant is experiencing significant depressive symptomology. The PHQ is given during routine diabetes clinic visits and data from the measure will be entered into REDCap when available. The diabetes clinical team addresses elevations on the PHQ during routine clinical care and thus if elevations are addressed during clinic, no further action will be taken by our research team. However, if the PHQ is only administered via the research protocol and there is an elevation on the PHQ, the following actions will be taken. REDCap is now programmed to send an alert if anyone scores ≥ 10 (considered moderate risk) on the PHQ. The alert will be sent to the site PI, supervising psychologist and coordinators. Results will also be communicated to the primary caregiver or adult participant within 3 business days of the elevation and appropriate referrals to outpatient mental health services will be provided, as necessary. In the instance a family is unable to be contacted within 3 business days despite several attempts, a letter (see Appendix P) will be sent to the address on file detailing this information. Additional details on these procedures are provided in Appendix E.

There is also the risk of possible loss of privacy of data or loss of confidentiality. These risks are inherent in all research studies, and a statement to this effect will be included in the informed consent/assent documents. Every effort will be made to ensure that all participant information will be kept confidential. A majority of this study is going to be conducted via Zoom sessions. Participants will access or receive information from several different sources including REDCap, Tidepool, Diabetes Journey site, T1Dtoolkit site, and Zoom for Healthcare. De-identified ID numbers will be used when possible for the sites. For example, enrolled participants will be assigned a secure login ID and password by the study staff to access measures via REDCap and/or to upload diabetes devices through Tidepool or other platforms. Each site will only be able to see their own site's participants in REDCap, with the exception of the lead site (CCHMC). Additionally, The University of Florida PI and her study team will manage the study for the University of Colorado Barbara Davis Center. They are all non-paid employees of the University of Colorado Barbara Davis Center and are authorized to have access to the University of Colorado Barbara Davis Center data. The University of Florida and University of Colorado Barbara Davis Center teams will meet weekly to review the study protocol, monitor recruitment and discuss other study related issues that may arise. Participants will be asked not to share their ID or password with anyone else. Use of Protected Health Information (PHI) on online measures will be minimized and participants will not be asked to enter their last name, date of birth, or medical record number on the online measures. When the study is complete,

the content of the site will be taken down. Setup is consistent with HIPAA guidelines and was designed to support projects that contain PHI and are subsequently subject to compliance with federal and state regulations regarding data of this type. Similarly, the Wordpress and T1Dtoolkit sites for the DJ modules will be linked to their study ID and there will be no identifying information listed in this site. Similarly, although Zoom for Healthcare is HIPAA compliant, participants will be required to login to the secured Zoom server for sessions and will be provided with the Zoom link to their email accounts. This information and protection of the participant's identity will be clarified in the informed consent and assent forms. We will provide each participant with a unique anonymous Tidepool username and password (See Appendix I). Finally, because interventionists can be from CCHMC or the University of Florida, participant information to conduct intervention sessions will be shared with the interventionist and appropriate supervisor in order to contact them.

To communicate study related information across sites, our team will be using Trello, a task management system that is frequently used by research teams. No identifying information will be entered into the Trello system; however, we will be tracking participants through the study procedures using their study ID.

Notably, the only place the study ID will be linked to the name and demographics is the participant database, which is password protected, individually, at each site by the research team. No other individuals outside of the IRB-approved research team from both sites will have access to this participant database.

11. RISK/BENEFIT ANALYSIS

There is minimal risk associated with study participation. If participants feel distressed as a result of their participation, they will be encouraged to discontinue. The PI and site PIs or their designee will be available to participants during study participation to assess for discomfort, safety, and risk, as needed. The minimal risks of this study do not outweigh the potential indirect benefits that may be gained through increasing knowledge about best practices for improving adherence barriers to treatment in adolescents with T1D.

12. DATA SAFETY AND MONITORING

This is a multisite observational study and is considered minimal risk. Safety monitoring will occur at the level of the multiple PIs due to the minimal risk nature of the study. See Appendix E for details of the NIDDK approved data safety and monitoring plan.

13. PRIVACY AND CONFIDENTIALITY

All study personnel have been trained in data safety and monitoring, privacy and confidentiality, minimizing risks related to loss of privacy and confidentiality. We will closely monitor performance of our research personnel to ensure the strictest standards. Additional information related to privacy and confidentiality is noted above in section 10.

13.1 Data De-Identification: All data will be de-identified with the use of unique assigned study identifier codes. No other identifying data such as address, phone numbers, social security number, or zip code will be entered on electronic measures. Electronic data files (including downloads of data from REDCap measures) will only identify participants via study identifier codes and will be password protected. Electronic data files will be maintained on CCHMC hard drives.

Because this research study involves payment for participation, we are required by Internal Revenue Service (IRS) rules to collect and use participant's social security number (SSN) or taxpayer identification number (TIN) in order to track the amount of money that we pay them. Unless they have given specific permission for another use of their SSN or TIN related to this research study, we will only use their SSN or TIN to keep track of how much money we pay them and their SSN or TIN will not be used as part of this research study.

13.2 Data Storage and Management

Informed consent/assent documents and all electronically collected data will be maintained in REDCap, a secure web-based platform, and in a password protected electronic database on CCHMC hard drives. Device data downloaded from Tidepool (a HIPAA compliant website used routine for clinical care) will be kept in password protected electronic databases at CCHMC. CCHMC is the Primary Site and will manage all the final deidentified data. Paper informed consent/assent documents will be maintained in locked storage cabinets, if they are needed, and will be kept separate from participant data.

Trello (www.trello.com), a web-based project management tool, will be used to coordinate study-related tasks across sites. No identifiable patient information will be saved in this platform. Medical chart data will be collected by trained study staff at each site under the supervision of the PI or site PI. These risk protection methods have been effectively used by the PI and her collaborators for numerous studies.

Individual data will not be available to anyone not directly associated with the study. All study personnel have been trained in data safety and monitoring, privacy and confidentiality, minimizing risks related to loss of privacy and confidentiality. We will closely monitor performance of our research personnel to ensure the strictest standards. Study-related information will not be released without written permission of the participant.

14. COST OF PARTICIPATION

There are no costs for participation in this research study. Participants will be responsible for the usual costs of medical care.

15. PAYMENT FOR PARTICIPATION

Caregivers will be compensated for participation in the study in the form of a reloadable debit card (ClinCard). They will receive a handout that will explain how to use this card. A graduate incentive schedule will be as follows:

	Adolescents		Caregivers
	Questionnaires	Device Download	Questionnaires
Phase 2 (n=256)			
Baseline	\$10	\$10	\$10
Post-treatment	\$15	\$10	\$10
Follow-up	\$20	\$10	\$10
TOTAL	Up to \$75		Up to \$30

References

6. Professional Practice Committee: Standards of Medical Care in Diabetes-2018. *Diabetes Care*. Jan 2018;41(Suppl 1):S3.

Statistical Analysis Plan

**Diabetes Journey: An Adolescent Adherence Barriers Intervention
Study Protocol**

Clinicaltrials.gov NCT04404556

Unique Protocol ID: 2020-0162

Date: November 21, 2024

Co-PIs: [name] and [name]

Biostatistician: [name]

Introduction

Type 1 diabetes (T1D) treatment adherence is complex and involves glucose monitoring, counting carbohydrates, and intensive insulin delivery via injections or insulin pump in response to food intake, exercise, and illness to achieve near-normal blood glucose. Overwhelming evidence demonstrates that T1D treatment adherence is challenging, especially during adolescence, which can lead to suboptimal glycemia (e.g., HbA1c) that severely compromises health, including acute (e.g., diabetic ketoacidosis) and long-term complications (e.g., kidney failure), and in some cases, premature death. While several interventions have been developed for adolescents with T1D, none have focused on adherence barriers, a novel patient-reported outcome (PRO). The Barriers to Diabetes Adherence questionnaire, assesses these important targets for tailored adherence interventions, including stress/burnout and time pressure/planning (executive dysfunction). These adherence barriers are significantly associated with non-adherence, higher HbA1c, and lower health-related quality of life (HRQOL); however, no interventions have targeted stress/burnout and time pressure/planning in research or clinical practice. The overall objective of this study was to use PROs (e.g., adherence barriers) to identify patient-centered intervention targets that will guide the integration of a novel tailored intervention into clinical care to improve adherence, HbA1c, and HRQOL.

We conducted a pilot randomized controlled clinical trial (RCT) of the *Diabetes Journey* intervention that was developed iteratively using feedback from user-centered experiences and experts in T1D. Our goal was to evaluate the initial efficacy, feasibility, and acceptability of *Diabetes Journey* targeting adherence barriers (stress/burnout, time pressure/planning) in adolescents with T1D. Secondary outcomes include adherence, HbA1c, and HRQOL.

In March 2022, due to the COVID-19 pandemic and slow recruitment, we made a number of changes, approved by NIDDK, to our protocol. For Aim 3, these included lowering our age eligibility to 12 years old, making the age range 12-17 years. We also eliminated our exclusion criteria regarding use of metformin and asthma medications as these had no impact on the science of our study. We also reduced the sample size from N=256 to N=190 based on our preliminary data and considered the study a pilot trial. We eliminated the final follow-up assessment from required to optional, and reverted to 1:1 randomization for the treatment and control group allocation. Finally, to minimize missing data, we modified procedures to ensure our primary outcome was captured at our primary endpoint (Follow-up 1) at a minimum to ensure we could make valid causal inferences. Thus, we made the Barriers to Diabetes Adherence questionnaire the only required measure for completion prior to randomization or moving to subsequent timepoints. Because HbA1c could be collected from chart reviews, we were confident about obtaining these data, as well as basic measures of adherence from the medical chart.

Study Hypotheses

Primary Aim: Examine feasibility, acceptability, and preliminary efficacy of *Diabetes Journey* to reduce adherence barriers (PRO) in adolescents with T1D over time.

Hypothesis: The treatment group will find the treatment acceptable and feasible and demonstrate significant improvements in barriers, adherence, HbA1c, and HRQOL.

Study Design

This study was a multi-site RCT designed to evaluate the efficacy of the *Diabetes Journey* mHealth intervention aimed at reducing barriers to T1D self-management among adolescents. These barriers include stress/burnout, executive dysfunction, and time management challenges. Participants were randomized into two groups: *Diabetes Journey* intervention or Enhanced Standard of Care, using stratified block randomization. The study was conducted across multiple sites and followed participants at baseline, post-treatment, and follow-ups at 6 and 12 months.

Adolescents endorsing clinically elevated adherence barriers during routine clinical care (primary outcome and intervention target-Barriers to Adherence scale) were randomized to: 1) *Diabetes Journey* or 2) Enhanced Standard of Care. For *Diabetes Journey*, each mHealth module accompanied a telemedicine session to review skills and problem-solve adolescent-identified goals with a therapist. For Enhanced Standard of Care, adolescents received handouts and phone calls from a certified diabetes educator.

Power and Sample Size Estimates

Initially, sample size estimates were based on the Epilepsy Journey study, which found moderate to large effect sizes from baseline to 6-month follow-up, ranging from $d = 0.55$ to $d = 0.93$ for the Global Executive Composite Score of the Behavior Rating Inventory of Executive Function. We also used Barriers to Diabetes Adherence questionnaire data collected as part of routine care from adolescents who attended T1D medical appointments at Cincinnati Children's Hospital Medical Center (CCHMC) from 2016-2017, which showed improvement across one year on Stress/Burnout and Time Pressure/Planning subscales ($d = 0.19$). A Monte Carlo simulation in Mplus with $n = 5,000$ replications was conducted assuming: 1) proper handling of missing data; 2) 25% attrition; 3) standardization of all analysis variables; 4) $>30\%$ of the error variance in our primary outcome ($R^2 = 0.30$) explained by baseline Barriers to Diabetes Adherence questionnaire scores and covariates; 5) smallest effect size from our preliminary work in the treatment group (i.e., $d = 0.55$); and 6) small improvement in Enhanced Standard of Care ($d = 0.19$). Our analysis indicated $>80\%$ power to detect a follow-up group difference effect size of $\Delta d = 0.36$ (where $\Delta d = 0.55 - 0.19$) with a total sample size of $N = 256$, with $n = 100$ in Enhanced Standard of Care and $n = 156$ in *Diabetes Journey*.

Given recruitment challenges and the resulting changes to eligibility and randomization, we decided to focus on the overall *Diabetes Journey* versus Enhanced Standard of Care difference at our primary endpoint, instead of powering for treatment subgroup comparisons. Using the same effect size estimates and assumptions in the original power analyses, but assuming a 1:1 randomization to only two groups, we determined that reducing the sample size from $N = 256$ to $N = 190$ ensured $>80\%$ power to detect a follow-up group difference effect size of $\Delta d = 0.36$, resulting in final group sizes of $n = 110$ in *Diabetes Journey* and $n = 80$ in Enhanced Standard of Care.

Randomization

At baseline, all participants who met inclusion/exclusion criteria (e.g., elevations on the Stress/Burnout and/or Time Pressure/Planning subscales of the Barriers to Diabetes Adherence questionnaire) were randomized to either the control group (i.e., Enhanced Standard of Care) or treatment group (i.e., *Diabetes Journey*). We used stratified block randomization with two strata and blocks of size 2 or 4 chosen randomly within each stratum. Stratification was based on baseline HbA1c (i.e., $>9\%$ or $<9\%$), site (i.e., CCHMC or University of Florida/University of

Colorado's Barbara Davis Center for Diabetes), and Barriers to Diabetes Adherence elevation type within the treatment arm (i.e., elevated on one or both of the subscales). The HbA1c criterion was selected because the average HbA1c in 13-17 year olds with T1D in the US is 9%, which resulted in comparable sample sizes above and below 9%. In addition, although the American Diabetes Association recommends an HbA1c <7%, very few adolescents achieve this. Site was chosen to ensure balance for any site-related differences. The randomization list was held by an individual independent of the study to reduce any potential biases. Those who were randomized were notified of their randomization status after completion of the baseline questionnaires so intervention materials could be provided immediately.

Measures

Definitions and Derivations (numbers at the end of variable names represent timepoint: 0=baseline; 1=post-treatment, 2=follow-up1 and 3=follow-up2)

Barriers to Diabetes Adherence (BDA) (Mulvey et al., 2011)				
Subscale	Descriptor	Items	Range	Interpretation
bdastress	BDA Stress and Burnout Subscale	4	1-5	↑ scores ↑ stress and burnout
bdatime	BDA Time Pressure and Planning Subscale	5	1-5	↑ scores ↑ planning barriers
bdastress0, bdastress1, bdastress2, bdastress3, bdatime0, bdatime1, bdatime2, bdatime3				

Type 1 Diabetes and Life (T1DAL) Adolescent 12-17 (Hilliard et al., 2019)				
Subscale	Descriptor	# of items	Range	Interpretation
t1daltotal	T1DAL Adolescent Total Score	23	0-100	↑ scores ↑ HRQOL
t1daltemotion	T1DAL emotional experiences and daily activities	11	0-100	↑ scores ↑ HRQOL
t1dalhandling1d	T1DAL Handling Diabetes	6	0-100	↑ scores ↑ HRQOL
t1daltpeer	T1DAL Peer Relationships	3	0-100	↑ scores ↑ HRQOL

t1daltfamily	T1DAL Family Relationships	3	0-100	↑ scores ↑ HRQOL
t1dalhandlingt1d0, t1dalhandlingt1d1, t1dalhandlingt1d2, t1dalhandlingt1d3, t1daltpeer0, t1daltpeer1, t1daltpeer2, t1daltpeer3, t1daltfamily0, t1daltfamily1, t1daltfamily2, t1daltfamily3, t1dalemotionr0, t1dalemotionr1, t1dalemotionr2, t1dalemotionr3, t1daltotalr0, t1daltotalr1, t1daltotalr2, t1daltotalr3				

Additional Variables

- a1c0, a1c1, a1c2, a1c3 (Hemoglobin A1C value)
- Condition (0=ESC, 1=Diabetes Journey)
- site (1=CCHMC; 2=UF, 3=BDC)
- age (continuous variable from 12-17 years old)
- sex (0=male; 1=female)
- insur (0=public; 1=private, 2=both, 3=uninsured)
- cgm (0=No CGM device, 1=Yes CGM device)
- timedx (continuous variable - T1d duration)
- race (0=Native American/Alaskan; 1=Asian, 2=Native Hawaiian/Pacific Islander; 3=Black, 4=White, 5=More than one race, 6=Other)
- ethn (0=Non-Hispanic; 1=Hispanic)
- rel (0=Mothers/StepMothers; 1=Fathers/Stepfathers, 2=Legal Guardian, 3=Grandmother, 4=Grandfather, 5=Other)
- mstatus (0=Single, 1=Married, 2=Separated, 3=Living with Someone, 4=Divorced, 5=Widowed)
- edu (0=6th grade or less, 1=7-8th grade, 2=9-11th grade, 3=High school graduate, 4=Some college or certificate course, 5=College Graduate, 6=Graduate or Professional degree)
- meth (0=Premixed/conventional insulin, 1=Multiple Daily injections, 2=Insulin Pump)

Subscale	Descriptor	Items	Range	Interpretation
cefisaya_distress	COVID-19 distress score	1	1.0-10.0	↑ scores ↑ distress
cefisaya_impact				

Statistical Analyses

Primary Aim Analysis Plan:

An intent to treat approach will be undertaken for all analyses. We will examine the data for intervention group comparability using chi-square tests for categorical variables (e.g., biological sex, insurance status, technology use) and t-tests for continuous variables (e.g., age, T1D duration) prior to analysis of the primary outcomes. Should we observe intervention group

differences at baseline on any variables, these variables will be added to the outcome models as covariates.

Our primary hypothesis examines group differences at the 6-month follow-up (i.e., primary end point) given that we expect participants to have made the most significant gains from the intervention after implementing the acquired skills for some time. Two separate Analysis of Covariance models (one for each barrier subscale) will be used to test the primary hypothesis that the *Diabetes Journey* intervention group will demonstrate significantly lower barriers compared to the Enhanced Standard of Care group at 6-month follow-up, after controlling for baseline barriers. For secondary outcomes (i.e., HRQOL, T1D self-management behaviors, HbA1c), the same analytical approach will be used, with baseline values of the respective outcome included as a covariate. To evaluate the treatment effect on our primary and secondary outcomes across time, we will employ Generalized Estimating Equations (GEE), while controlling for baseline covariates.

Handling Missing Data

Missing data will be addressed using full information maximum likelihood (FIML) under the assumption of data missing at random (MAR) in the ANCOVA models. For the longitudinal GEE models, we will use multiple imputation to address missing data under the assumption that the data are Missing at Random (MAR). The imputation will use chained equations (mi impute chained) with relevant predictors to generate 100 imputed datasets.

Variables:

Outcome variables:

- Primary: BDA subscale scores for stress and time pressure (bdastress, bdatime)
- Secondary: alc, T1DAL subscales and total score (t1dalhandlingt1d, t1daltpeer, t1daltfamily, t1dalemotionr, t1daltotalr)
- **Group (independent variable):**
 - condition (0 = ESC, 1 = DJ)
- **Timepoints:**
 - time (post-treatment = 1, follow-up 1 = 2, follow-up 2 = 3)
- **Covariates:**
 - age (continuous)
 - sex (categorical, 0 = male, 1 = female)
 - insurance (insur, 0=public, 1=private)
 - time since dx (timedx, continuous)
 - use of technology (cgm yes = 1, cgm no = 0)
 - adolescent reported COVID impact scores at baseline (cefisaya_impact; continuous)
 - baseline outcome scores (outcome scores measured at time 0; continuous)
 - site (dummy coded as s1, s2; UF, BDC, CCHMC)
- **Correlation Structure (for GEE model):** Exchangeable correlation structure (to account for correlations within participants over time).

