Satisfaction and Acceptability Questionnaire	Y/C			X	X
Device Downloads	Y		X	X	X
Fingerstick Blood Sample	D		X	X	X
Medical Record/Patient Record	D		X	X	X

8.2 Sample Size Considerations and Power Analysis:

Sample size for this study is based on our preliminary work with this intervention in epilepsy (i.e., Epilepsy Journey), which found moderate to large effect sizes from baseline to 6-month follow-up, ranging from $d = 0.55$ to $d = 0.93$ for the Global Executive Composite Score, the composite measure of the Behavior Rating Inventory of Executive Function, which represented our barriers outcome of interest. Additionally, preliminary data on our primary outcomes collected at CCHMC from 2016-2017 (i.e., Stress/Burnout and Time Pressure/Planning subscales) show that our patients improve slightly over one year with Enhanced Standard of Care, corresponding to an effect size of $d = 0.19$. A Monte Carlo simulation in Mplus with $n = 5000$ replications was conducted assuming: 1) proper handling of missing data; 2) 25% attrition; 3) standardization of all analysis variables; 4) at least 30% of the error variance in our primary outcome ($R^2 = 0.30$) being explained by baseline barriers scores and covariates; 5) we will observe the smallest effect size from our preliminary work in the treatment group (i.e., $d = 0.55$); and 6) we will observe a small improvement in our control group ($d = 0.19$). **Recent interim analyses and meetings with our NIH program officer have yielded a change in our study design from a fully powered RCT to detect subgroup differences to a pilot RCT focused on feasibility, acceptability, satisfaction and preliminary efficacy differences between the control and treatment groups. These new analyses indicate the need for a total sample size of $n=190$ ($n=95$ in the control group and $n=95$ in the treatment group).**

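### The reported 110:80 split does not fit the one randomisation scheme described, and no model adjusts for randomisation phase although allocation was changed to 1:1 during recruitment

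*SAP*

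**What the plan says.** The SAP's Introduction lists changes made in March 2022 because of the pandemic and slow recruitment. One is that the study "reverted to 1:1 randomization for the treatment and control group allocation". The same package lowered the minimum age to 12, dropped the exclusions for metformin and asthma medication, cut the sample from 256 to 190, and changed procedures to secure the primary outcome at its endpoint.

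Under Power and Sample Size Estimates, the SAP gives the original plan as 156 in Diabetes Journey and 100 in Enhanced Standard of Care. It then describes the revised calculation as "assuming a 1:1 randomization to only two groups" and, in the same sentence, as "resulting in final group sizes of $n = 110$ in *Diabetes Journey* and $n = 80$ in Enhanced Standard of Care". Protocol section 8.2 plans 95 per arm.

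The SAP's Randomization section describes one scheme, with "blocks of size 2 or 4 chosen randomly within each stratum". Protocol section 8 describes the same scheme. Neither section mentions an earlier ratio or two periods.

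In the Primary Aim Analysis Plan, the ANCOVA compares the arms at 6 months "after controlling for baseline barriers". The covariate list is age, sex, insurance, time since diagnosis, CGM use, baseline COVID impact, baseline outcome and site. A further rule covers arm "differences at baseline on any variables, these variables will be added to the outcome models as covariates".

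**The concern.** Two things do not fit together. First, the final split cannot come from the only scheme described if that scheme was 1:1 throughout, so a reader cannot tell how 110:80 arose. Second, the likely explanation, a change of ratio part-way through, has a consequence for the analysis that the SAP does not address.

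Randomisation protects the arm comparison within each allocation ratio. When patients randomised under different ratios are pooled, one arm holds a larger share of early recruits. Any difference between early and late patients in 6-month BDA scores that the covariates do not capture then enters the treatment estimate. Such a difference is plausible because eligibility and outcome-capture procedures changed in the same package. Phase may also predict missingness, which bears on the missing-at-random assumption behind both FIML and multiple imputation.

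**Working it through.** **1. Can the described scheme give 110:80?**

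Reported excess: 110 - 80 = 30. In 1:1 blocks of 2 or 4, the arms differ by at most 2 within a stratum (half of an unfinished block of 4). The maximum overall excess is therefore 2 x number of strata.

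| Reading | Strata | Maximum excess | Most extreme split |
|---|---|---|---|
| "Two strata" taken literally (SAP, protocol) | 2 | 4 | 97:93 |
| SAP factors: HbA1c 2 x site 2 x BDA type 2 | 8 | 16 | 103:87 |
| Protocol factors: HbA1c 2 x site 3 x BDA type 2 | 12 | 24 | 107:83 |

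Reaching 30 needs at least 15 strata (30/2). In 20,000 simulated trials of 190 patients for each stratum count, the largest differences seen were 4, 8 and 12. The reported split is not reproduced.

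**2. What phase mix would give 110:80?**

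The documents do not state the earlier ratio. Assume two phases, with treatment probability r for the first x patients and exactly 1:1 afterwards:

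x·r + (190 - x)·0.5 = 110, so x = 30/(2r - 1).

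| Assumed earlier ratio | r | Early patients x | Early DJ : control | Early share, DJ vs control | Difference |
|---|---|---|---|---|---|
| 1.56:1 (156:100) | 156/256 | 137.1 | 83.6 : 53.6 | 76.0% vs 67.0% | 0.090 |
| 2:1 | 2/3 | 90 | 60 : 30 | 54.5% vs 37.5% | 0.170 |
| 3:1 | 3/4 | 60 | 45 : 15 | 40.9% vs 18.8% | 0.222 |

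**3. Bias if phase is left out**

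Bias = difference in early share x residual early/late difference in the outcome. The shifts of 0.2 and 0.5 SD are assumptions.

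| Earlier ratio | Bias at 0.2 SD (% of 0.36) | Bias at 0.5 SD (% of 0.36) |
|---|---|---|
| 1.56:1 | 0.018 (5.0%) | 0.045 (12.5%) |
| 2:1 | 0.034 (9.5%) | 0.085 (23.7%) |
| 3:1 | 0.044 (12.3%) | 0.111 (30.8%) |

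**4. Type I error**

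With the SAP's R² of 0.30, SE = √0.70 × √(1/110 + 1/80) = 0.123. With 25% attrition, SE = 0.123/√0.75 = 0.142. Two-sided 5% testing is assumed because the documents state neither alpha nor sidedness. With z = bias/SE, the error rate is P(Z > 1.96 - z) + P(Z < -1.96 - z). Over both SEs and the first two ratios, it is 5.2-5.9% at a 0.2 SD shift and 6.2-10.7% at 0.5 SD. At 3:1 and 0.5 SD with no attrition, z = 0.111/0.123 = 0.90 and the rate is about 14.7%.

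**5. Would the baseline-difference rule pick phase up?**

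Phase is not among the variables the SAP defines. If it were tested anyway, the squared arm-phase correlation is 0.0099 (1.56:1) or 0.0284 (2:1). Chi-square = 190 x 0.0099 = 1.87 (p = 0.17) or 190 x 0.0284 = 5.40 (p = 0.02). At the 0.05 level the rule would leave phase out in the first case.

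**The case against.** The strongest reply is that the SAP discloses the change. The 103:87 and 107:83 limits presuppose 1:1 throughout, and the Introduction says that was not so. An unequal split is what a disclosed change would produce, so the Randomization section is incomplete and the figure is not impossible. That is fair as far as it goes. But disclosure gives no earlier ratio and no counts, and it does not adjust the analysis.

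The limit also assumes that each stratum's list ran once. If the lists were restarted at the change, 8 strata x 2 periods x 2 = 32, which exceeds 30. That would need nearly every list in both periods to stop at its largest excess in favour of Diabetes Journey, which is very improbable. It is also possible that the final group sizes are not the numbers randomised, and that a return to 1:1 implies an even earlier 1:1 period. These points stand as uncertainties, and only counts by phase and arm can settle them.

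Blocks of 2 or 4 cannot deliver 1.56:1 or 2:1 exactly, so those scenarios need a different scheme for the early period. A block of 4 can deliver 3:1, and under that ratio the potential bias is larger.

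On size, the covariates already include age, site, CGM use, COVID impact and baseline BDA. Age deals directly with the lowered age limit. A residual shift of 0.5 SD would be large, and nothing in the documents shows one. This stands: the bias may be small or zero. The listed covariates are still only partial stand-ins for phase. The phrase about relevant predictors in the imputation text does not exclude phase, but does not commit to it either.

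**Conclusion.** The concern holds. An excess of 30 is beyond what one 1:1 scheme with blocks of 2 or 4 can give for any stratum count the documents support, and no model term represents randomisation phase.

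The likely effect on the primary comparison is modest. Across the 1.56:1 and 2:1 scenarios it is 0.018 to 0.034 SD for a 0.2 SD residual phase difference, and 0.045 to 0.085 SD for 0.5 SD. These figures rest on an assumed earlier ratio, two phases, exact 1:1 balance after the change and an assumed shift. The direction is unknown. A change of ratio during recruitment is itself an inference, though a strong one, from the March 2022 text, the 156:100 plan and the final split.

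**What to change.** - **Randomization section (SAP and protocol):** state each allocation ratio actually used, the block sizes that went with it, the date of change, and the numbers randomised by phase and arm.
- **Group sizes:** reconcile 110:80 with the protocol's 95:95 and with the 1:1 power assumption, keeping that assumption labelled as what was assumed at the time.
- **Models:** add randomisation phase, with one level for each allocation ratio used, as a fixed covariate in the ANCOVA and GEE models, and name it in the imputation model.
- **If only one ratio was ever used:** say so and explain 110:80. The phase term is then not needed for this reason.

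The statistical cost is one degree of freedom per added level and a small loss of precision. The SE grows by 1/√(1 - 0.0099), about 0.5%, or 1/√(1 - 0.0284), about 1.5%. At an effect of 0.36 and R² of 0.30, two-sided 5%, power moves from 83.4% to 83.0% (1.56:1) or 82.3% (2:1) without attrition, and from 71.8% to 71.3% or 70.5% with 25% attrition. That is a loss of about 0.4 to 1.2 points. At 3:1 it would be 2.1 to 2.5 points. The rest is wording in both documents and the randomisation dates.
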